HMC RESEARCH PROTOCOL

Study Title:	Anesthetic Management for Burn Injuries During SARS-CoV-2
Local IRB Serial number	MRC-01-20-1074

Contents

1. Synopsis	2
2. Abbreviations and Acronyms	2
3. Introduction / Background	3
4. Objectives	4
5. Indicate if this is a retrospective data review.....	4
6. Study Methodology	4
7. Study Population and Study Setting/ Location	4
8. Study procedures.....	5
Study Duration and Timelines	5
Informed Consent	5
Risk	5
Bio-Specimens & Sample Collection.....	5
Outcomes.....	5
Data Collection, Data Management& Confidentiality	6
Subject Withdrawal/ Withdrawal of Consent	6
9. Statistical Consideration and Data Analysis.....	6
10. Adverse Event Reporting	7
11. Ethical Consideration	7
12. Sponsor, Funding & Collaborator Information.....	7
13. Dissemination of Results and Publication policy.....	7
14. Appendices	7
15. References	7-8

1.Synopsis

Objective Anesthetic management of burn patients is a real challenge to the anesthesiologist. Recently, in the presence of COVID-19 epidemic, we tried to manage safely our patients and provide protection for our health care professionals. There is a lack of information about Survival of burn patients under these conditions.

Aim of this work:

Primary outcome is to investigate survivals, ICU admission and length of hospital stay of those critical patients.

Secondary outcome is to analyses perioperative factors that affected their survival outcome.

2.Abbreviations and Acronyms

Severe acute respiratory syndrome coronavirus-2, (SARS-Cov-2), coronavirus disease 2019, COVID-19; American Society of Regional Anaesthesia and Pain Medicine, ASRA; European Society of Regional Anaesthesia and Pain Therapy, ESRA

3. Introduction / Background

The rapidly spreading severe acute respiratory syndrome coronavirus-2 (SARS-CoV-2) the causative agent of coronavirus disease 2019 (COVID-19) epidemic is attacking the whole world and exaggerating an economic crisis (1). It is transmitted via contact with respiratory droplets that exposes anaesthetists to the risk of viral infection during their routine work (2),(3).

All countries have implemented protective and preventive measures which subjected persons to stay longer period at home. A Brazilian study found that spending more time in the domestic environment and, consequently, leading to a greater exposure to sanitizer products, which contain ethanol and hydrogen peroxides that can lead to burn injuries during the pandemic period of COVID-19 (4),.

Many burn centers have revised their policy during COVID-19 pandemic (5),(6). Burns are an acute emergency condition, and burn management needs to be initiated before COVID-19 infection status can be confirmed. Our institute already developed an algorithm for protection during COVID-19 infection. However, anesthesia management is challenge for burn patient particularly if the patient is suspected or diagnosed to be positive for corona virus.

In the era of COVID-19, Both the American Society of Regional Anaesthesia and Pain Medicine (ASRA) and the European Society of Regional Anaesthesia and Pain Therapy (ESRA) established a joint statement which recommends neuraxial and peripheral nerve blocks for patients with COVID-2019 infection and describe the benefits of regional anesthetic and analgesic techniques over general anaesthetics especially in patients with underlying metabolic derangements such as burns (7). Those critical patients with COVID-19 were subjected to coagulation abnormalities which may affect their survivals (8).

Aim of our Study:

Primary outcome is to investigate survivals, ICU admission and length of hospital stay of those critical patients.

Secondary outcome is to analyses perioperative factors that affected their survival outcome.

4. Objectives

In this section provide a clear statement of the primary and any secondary objectives of the study

To investigate survivals, ICU admission and length of hospital stay of those critical patients.

And to analyze perioperative anesthetic factors that affected their primary outcome.

5. Indicate if this is a retrospective data review

- **Retrospective Chart/data Review** *(Retrospective means the data is already in existence when the project is submitted to the IRB for initial review.)*
- **Provide the date range of the chart review** *(if this is a retrospective chart review, the end date must come before the submission date April 1, 2020, and November 16, 2020.)*

6. Study Methodology

Patients who had the burn graft surgery at Al Wakrah Hospital; Hamad Medical Corporation between from April 1, 2020, and November 16, 2020. **Planned sample size will include all COVID-19 positive and negative cases. Our institution as Al Wakrah Hospital is the ONLY center at HMC which deals with those unique Burn patients allover Qatar. By increasing sample size, we can get our expected results statistically.**

Data Source

The electronic medical record (Cerner) used in order to identify patients who match study defined criteria. We can Collect data directly from Cerner to excel sheet

Variable Abstraction

Patient demographic and clinical data will be collected including age, morbidities, presenting symptoms, physical examination, laboratory investigations, intraoperative data, type of surgery, postoperative course, survival, and length of hospital stay and follow up.

In addition, the type of anesthesia is also included as factor for further complications ex general anesthesia, spinal or combined spinal epidural type.

Retrospective full reviewing of their medical illness and chart laboratory and investigations will be collected after getting approval of MRC and IRB committee.

7. Study Population and Study Setting/ Location

All adult patients who had undergone burn graft surgery at Al Wakrah (AWH) Hospital; Hamad Medical Corporation between April 1, 2020, and November 16, 2020. We will include all Consecutive Adult patient underwent burn grafting surgery at AWH either

they are COVID positive or negative.

8. Study procedures

Provide an outline and describe in detail the processes and operations of the study, including logistics

Study Duration and Timelines

Expected duration of the study & start times, stages of the study such as screening, treatment phase, visit numbers, etc

6 months data collection & another 6 months writing manuscript and trial to submission to a suitable journal

Informed Consent

Informed Consent will be waived for such a retrospective analysis.

Risk

This study has no physical, psychological, economic or societal harms that may befall a subject as a result of their data being included in this study.

Bio-Specimens & Sample Collection

Not applicable

Outcomes

Primary outcome is to investigate survivals, ICU admission and length of hospital stay of those critical patients.

Secondary outcome is to analyses perioperative anesthetic factors that affected their primary outcome.

Data Collection, Management&Confidentiality

a) Indicate below HOW study data will be collected for the proposed research.

Study Forms Study Database Study Web-Based/App Other

Please detail how study data will be coded:

Special encryption codes will be used to separate research data from subject identifiers and the data will be dealt with privacy and confidentiality. Each patient will be assigned a random code and any information relating to the patient will now only be related to the patient by the random code and not by their name or health card number. Then any link to the actual record will be destroyed after data collection is completed. The anonymized data set will be kept for at least 5 years after study completion. Data will be collected in excel format.

b) Describe below WHERE and HOW the study data is physically stored.

Primary investigator will store the electronic data on a password protected computer which is secured by a firewall. Data collection form will be kept in a safe cabinet. The anonymized data set will be kept for at least 5 years after study completion.

kept in a safe cabinet

c) Describe below WHO controls access to the study data

PI

d) Describe below WHO has access to the study data.

PI

e) Describe below HOW the study data is accessed.

The lead PI will have the control over the access to study data through password secured computers.

f) Will subject identifiers be shared outside of HMC? If YES describe below WHOM the study data is shared

No

Subject Withdrawal/ Withdrawal of Consent

Not applicable

9. Statistical Consideration and Data Analysis

Descriptive statistics will be used to summarize all demographic, clinical, laboratory

tests, intraoperative data, postoperative course and outcomes. The normally distributed data and results will be reported with mean and standard deviation (SD); the remaining results will be reported with median and interquartile range (IQR). Categorical data will be summarized using frequencies and percentages.

Survival can be performed using Kaplan Meir Curve; risk factors can be identified by using Univariate Analysis and Multivariate Logistic Regression Analysis.

All P values presented will be two-tailed, and P values <0.05 will be considered as statistically significant. All Statistical analyses will be done using statistical packages SPSS 22.0 (SPSS Inc. Chicago, IL) and Epi-info (Centers for Disease Control and Prevention, Atlanta, GA) software.

10. Adverse Event Reporting

No adverse events are expected.

11. Ethical Consideration

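### The secondary aim differs between sections, and where it links anaesthetic factors to ICU admission and hospital stay, neither outcome is limited to the time after the anaesthetic

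*Combined protocol and SAP*

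**What the plan says.** The secondary aim appears in two forms.

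- Synopsis (Section 1) and the aim in Section 3: "Secondary outcome is to analyses perioperative factors that affected their survival outcome".
- Section 4: "And to analyze perioperative anesthetic factors that affected their primary outcome". Section 8, Outcomes: "Secondary outcome is to analyses perioperative anesthetic factors that affected their primary outcome".

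The primary outcome in Section 8 is: "Primary outcome is to investigate survivals, ICU admission and length of hospital stay of those critical patients". The Synopsis and Section 3 list the same three components as primary. The disagreement is therefore only about which of them the factor analysis addresses.

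The cohort in Section 7 is defined by the operation: "All adult patients who had undergone burn graft surgery". The exposure is in Section 6, Variable Abstraction, where "the type of anesthesia is also included as factor for further complications". The same section lists among the items to abstract "postoperative course, survival, and length of hospital stay and follow up"; ICU admission is not named there. Section 9 gives the analysis: "Survival can be performed using Kaplan Meir Curve; risk factors can be identified by using Univariate Analysis and Multivariate Logistic Regression Analysis". It states no time origin, outcome window or covariates. Section 14 lists a data collection form, which is not among the supplied documents.

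**The concern.** The two forms of the secondary aim call for different analyses: one outcome or three. An analyst following the Synopsis and one following Section 8 would produce different results sections.

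Under the wider form there is a problem of timing. Patients enter the cohort by having had a graft, and the exposure is the anaesthetic given for it. In ordinary use, ICU admission means any during the hospital episode, and stay means days from hospital admission. Both then include ICU care and waiting days that came before the anaesthetic and cannot have been affected by it. If patients given general anaesthesia were more often in ICU before surgery, or waited a different time, that difference would appear as an association with the technique. Sections 4 and 8 speak of factors that affected the outcome, so such an association would be read as an effect.

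**Working it through.** **Text check.** The documents give no sample size, event rate or figure for ICU use or waiting time, so there is no figure of the plan's own to reproduce. Four places could fix the timing:

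- Section 8, Outcomes: lists the three components with no start or window.
- Section 6, post-operative course: listed as a separate item beside length of stay, so it does not define stay.
- Section 6, complications: undefined, and not tied to ICU admission or stay.
- Section 9: names methods without a time origin.

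None limits ICU admission or stay to the period after the anaesthetic.

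**ICU admission: size of the possible bias.** All inputs are assumptions. Let *pre* be the proportion with any ICU admission before surgery and *post* the risk of a new ICU admission after surgery, with *post* equal in both groups (true OR 1).

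P(any ICU) = 1 − (1 − pre)(1 − post)

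With post = 10%, pre = 30% (general) v 10% (regional):
- General: 1 − 0.70 × 0.90 = 0.37. Regional: 1 − 0.90 × 0.90 = 0.19.
- Crude OR = (0.37/0.63) / (0.19/0.81) = 2.50.

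| pre, general v regional | post | any ICU | crude OR |
|---|---|---|---|
| 10% v 10% | 10% | 0.19 v 0.19 | 1.00 |
| 20% v 10% | 10% | 0.28 v 0.19 | 1.66 |
| 30% v 10% | 10% | 0.37 v 0.19 | 2.50 |
| 40% v 10% | 10% | 0.46 v 0.19 | 3.63 |
| 30% v 10% | 5% | 0.335 v 0.145 | 2.97 |
| 30% v 10% | 20% | 0.44 v 0.28 | 2.02 |

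**Does adjustment for pre-operative ICU help?** Take 100 per group, pre 30% v 10%, post 10%, and expected counts.
- Pre-operative ICU stratum: 30 of 30 v 10 of 10 have the outcome. Both Mantel-Haenszel terms are 0, so the stratum contributes nothing.
- Other stratum: 7 of 70 v 9 of 90. OR = (7 × 81)/(63 × 9) = 567/567 = 1.00.

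The adjusted OR is 1.00. In a logistic model the coefficient for pre-operative ICU diverges, because everyone in that stratum has the outcome. The anaesthetic coefficient does not.

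**Precision.** SE(log OR) = √[1/(n₁p₁(1−p₁)) + 1/(n₂p₂(1−p₂))].
- Any ICU, 100 v 100 at 0.37 and 0.19: 37 + 19 = 56 events, SE 0.328.
- New ICU at 0.10 in both groups, among patients not in ICU at surgery:
  - all pre-operative ICU patients still there (70 v 90): 16 events, SE 0.531, ratio 1.62;
  - half still there (85 v 95): 18 events, SE 0.498, ratio 1.52;
  - none still there (100 v 100): 20 events, SE 0.471, ratio 1.44.
- Adjusting for any pre-operative ICU uses the same 70 v 90 informative patients: SE 0.531.
- With 50 per group and all still in ICU, events fall from 28 to 8 and the ratio is again 1.62.

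**Stay.** Total stay = pre-operative wait + post-operative stay. If mean post-operative stay is equal, the difference in mean total stay equals the difference in mean wait, day for day; with equal waits it is 0.

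**The case against.** The strongest reply is that the harm is conditional at each step. The wider wording must prevail, ICU and stay must be counted from before surgery, pre-operative ICU use or waiting must differ by technique, and the unseen data collection form must not already define the outcomes. This stands. It limits the point to what the wording permits, but the conflict between sections depends on none of it.

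A second reply is that the logistic regression in Section 9 could deal with the ICU part. It could, if pre-operative ICU were a covariate. A reader might infer that adjustment is useless because every pre-operative ICU patient already has the outcome. The calculation shows otherwise: that stratum drops out and the anaesthetic OR returns to 1.00. But Section 9 names no covariates, and the abstraction list does not name ICU admission or its dates.

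A third reply is that the study is a descriptive chart review. Figures for any ICU use and whole stay are indeed sound as description. Section 9, however, also plans a risk-factor analysis with significance tests.

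A reader might further infer that the survival comparison is biased by time before surgery. Section 9 does not say where the Kaplan-Meier clock starts or that curves will be compared by technique, so the documents do not support this; the start of the clock simply needs stating.

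**Conclusion.** The point holds as a defect of wording and definition that should be corrected before analysis. Two things rest on the text alone: the secondary aim is inconsistent across four sections, and no supplied text starts ICU admission or stay at the anaesthetic.

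The bias is a possibility, not a finding. Over the assumed inputs the crude OR for any ICU admission runs from 1.0 (equal pre-operative use) to 3.6, with 2.5 in the central example; the documents supply none of these rates. A reader might infer that the anaesthetic comparison is shown to be biased. The documents do not show that pre-operative ICU use or waiting differs by technique. A reader might also infer that the Synopsis and Section 3 leave out ICU admission and stay altogether. They do not: both list them as primary, and only their secondary aim is confined to survival. If that narrower aim is chosen, the ICU and stay problem does not arise.

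**What to change.** 1. Make the secondary aim the same in the Synopsis and Sections 3, 4 and 8.
2. For any association analysis, name one index graft surgery per patient as time zero and classify exposure by that anaesthetic. Measure stay from that surgery and start any survival clock there.
3. For ICU, choose one of two routes in Section 9: count new admissions after surgery among patients not in ICU at surgery, or keep any ICU admission and adjust for any pre-operative ICU admission in the planned logistic model. Under the assumed inputs the second gives OR 1.00, SE 0.53.
4. Keep any-ICU and whole-stay figures as description.
5. Check whether the data collection form already defines these outcomes, and make sure it records the dates of hospital admission, surgery, ICU entry and exit, discharge and death. Section 8 has the link to the record destroyed once data collection ends, so this must come first.

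The cost is wording, a few dates per patient from the same electronic record, and precision for ICU. In the assumed example with 100 per group, informative events fall from 56 to about 16 to 20 and the standard error rises by about 44% to 62%. The precision given up belongs to an estimate that is biased under those inputs. So few events will support very few covariates, and confounding by burn severity remains under either route.

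### The Kaplan-Meier survival analysis has no time origin, horizon or rule for patients discharged alive; censoring them at discharge would overstate in-hospital mortality

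*Combined protocol and SAP*

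**What the plan says.** The Outcomes part of Section 8 states: "Primary outcome is to investigate survivals, ICU admission and length of hospital stay of those critical patients". Section 9 then gives the survival analysis: "Survival can be performed using Kaplan Meir Curve". It leaves risk factors to univariate analysis and a multivariable logistic regression. No cumulative incidence, competing-risk, log-rank or Cox method is named. Section 9 also says that outcomes will be summarised descriptively, with frequencies and percentages for categorical data.

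The only data source, in Section 6 (Data Source), is the hospital record: "We can Collect data directly from Cerner to excel sheet". Section 6 (Variable Abstraction) lists among the items collected "intraoperative data, type of surgery, postoperative course, survival, and length of hospital stay and follow up". Follow-up is therefore an abstracted variable, but no length, schedule or source of vital status after discharge is given for it. Section 8 (data coding) adds: "Then any link to the actual record will be destroyed after data collection is completed".

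Nowhere do the documents state when survival time starts, to what day survival is reported, or what happens on the curve to a patient who goes home alive.

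**The concern.** Kaplan-Meier assumes that a patient censored on a given day has the same future risk of death as a patient who remains under observation. Inpatients are discharged because they have recovered. If discharge is taken as the end of observation, the risk set shrinks to the sickest long-stay patients, and each later death removes a large share of the remaining survival estimate. The curve then no longer estimates the proportion who die in hospital; 1-KM lies above it, increasingly so at later days.

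In a chart review that abstracts length of stay, censoring survivors at discharge is an easy default when no rule is written. At stake is the survival percentage read from the curve for a primary outcome. The timing also matters: once the link to the record is destroyed, missing vital status cannot be added.

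**Working it through.** **Figures in the plan.** The documents give no sample size, number of deaths, mortality or length of stay, so there is no stated figure to reproduce. Every rate and stay below is an assumption.

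**1. Mechanism, by hand.** Take 20 patients with deaths on days 10 and 40 and 18 discharged alive, 16 of them between those days. At day 10, 20 are at risk. At day 40, 20 − 1 − 16 = 3 are at risk.

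- Discharge censored: 1-KM = 1 − (19/20)(2/3) = 36.7%.
- Discharged survivors kept at risk: 1 − (19/20)(18/19) = 1 − 18/20 = 10%, which is simply deaths divided by patients.

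**2. Closed form.** Assume constant hazards, in-hospital mortality p = 10% and mean stay 30 days. The death hazard is hd = 0.10/30 and the discharge hazard is hr = 0.90/30.

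- 1-KM with discharge censored: 1 − exp(−hd·t).
- Cumulative incidence of in-hospital death: p·(1 − exp(−(hd + hr)·t)).
- Day 30: 1 − exp(−0.1) = 9.5% against 0.10·(1 − exp(−1)) = 6.3%.
- Day 90: 1 − exp(−0.3) = 25.9% against 0.10·(1 − exp(−3)) = 9.5%.

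**3. Simulation with more realistic stays.** 400,000 patients; 10% die in hospital; death times exponential; survivors' stay lognormal with mean 30 days and log-SD 0.6; survivors censored at discharge.

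| Mean day of death | Day 30: 1-KM | Day 30: true | Day 90: 1-KM | Day 90: true |
|---|---|---|---|---|
| 10 | 10.8% | 9.5% | 13.5% | 10.0% |
| 20 | 9.7% | 7.8% | 26.6% | 9.9% |
| 30 | 8.2% | 6.4% | 34.7% | 9.5% |

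The day-30 excess is 1.3 to 1.9 points. The day-90 excess is much larger, but under 2% of the cohort is still at risk then. With 5% mortality, day-90 1-KM runs from about 7% to 20%.

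**4. Effect of follow-up after discharge.** Same model with 10% mortality, no deaths after discharge, and follow-up unrelated to prognosis.

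- Survivors observed for a random 0 to 180 days after discharge: day-90 1-KM is 10.1% to 10.2%.
- Half observed for 90 more days and half censored at discharge: 10.8%, 12.0% and 12.3% for mean death days 10, 20 and 30.

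Even incomplete follow-up removes most of the bias.

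**5. Could deaths after discharge justify the higher figure?** Use the closed form with 5% in-hospital mortality and mean stay 21 days. Day-90 1-KM is 19.3% and cumulative incidence is 4.9%. The proportion discharged by day 90 is 0.95·(1 − exp(−90/21)) = 93.7%. For 19.3% to equal all-cause mortality, (19.29 − 4.93)/93.7 = about 15% of discharged patients would have to die by day 90.

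**The case against.** The strongest reply is that the condition is not in the plan. Discharge is never named as the censoring time, and "postoperative course, survival, and length of hospital stay and follow up" lists stay and follow-up as separate items, so observation beyond discharge is contemplated. This stands. A reader might infer that follow-up will exist only for patients who come back, but the documents do not say so, and step 4 shows that even partial follow-up leaves little bias. What remains is that follow-up has no stated length, completeness or vital-status source, so the plan does not show which case applies.

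Second, Kaplan-Meier is not the only summary of survival. Frequencies and percentages are planned for outcomes, and a crude proportion of deaths would not carry this bias. That also stands, although the plan does not commit to that proportion as the survival result, and a discharge-censored curve could contradict it.

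Third, a reader might infer that comparisons by anaesthesia type or COVID status would be distorted. Section 9 assigns risk factors to univariate analysis and logistic regression and names no log-rank test, stratified curve or Cox model. Logistic regression on death does not use the censoring time, so the documents do not support that inference.

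**Conclusion.** The point holds as a gap in specification with a conditional bias. What is certain is that Section 9 names Kaplan-Meier for a primary outcome on hospital-record data without a time origin, a horizon, a rule for discharge alive or a source of later vital status. If survivors are censored at discharge, 1-KM overstates in-hospital mortality. The direction was the same in every scenario run; the size rests wholly on assumed inputs. At 10% mortality and a mean survivor stay of 30 days, the excess is 1 to 2 points at day 30. Day-90 1-KM is 13% to 35% against about 10% true, in a tail with very few patients. With some follow-up after discharge, the day-90 figure falls to about 10% to 12%.

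It would be tempting to conclude that the reported survival will be badly wrong. The documents do not support that: they neither state discharge censoring nor give the figures needed to size it. The gap should be closed because it concerns a primary outcome, costs little to close, and cannot be repaired once the link to the records is gone.

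**What to change.** Replace the survival sentence in Section 9 with wording to this effect:

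- Survival will be reported as in-hospital mortality, n/N with an exact 95% confidence interval.
- The cumulative incidence of in-hospital death will be reported from the first graft, with discharge alive as a competing event.
- Kaplan-Meier, and any fixed-day mortality such as 30-day, will be reported only if vital status to that day is known for every patient and is abstracted before the link to the record is destroyed. No patient will be censored at discharge.

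The condition must cover 30-day mortality as well as the curve: under the stay distribution assumed in step 3, about 62% of survivors leave before day 30. Section 6 should also state how far follow-up extends and where vital status after discharge is found.

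The cost is a change of wording plus, if fixed-day results are wanted, abstraction of vital status to that day. When every stay is complete, cumulative incidence at day t is deaths by day t divided by the number of patients, so no new software is needed. The downside is that, without vital status after discharge, the conclusion is limited to in-hospital death.

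### Section 9 plans logistic regression for survival factors with no limit on model size and no provision for few deaths; if deaths are few, some odds ratios may not be finite

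*Combined protocol and SAP*

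**What the plan says.** Section 9 gives one clause to the factor analysis: "risk factors can be identified by using Univariate Analysis and Multivariate Logistic Regression Analysis". The decision rule is that "P values <0.05 will be considered as statistically significant", two-sided, and "All Statistical analyses will be done using statistical packages SPSS 22.0" and Epi-info. No penalised, exact or reduced-model version is named, so ordinary maximum likelihood is the natural reading, although the text does not use that term. The clause names no dependent variable.

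The outcome has to be read from other sections. The Synopsis and the aim in Section 3 state: "Secondary outcome is to analyses perioperative factors that affected their survival outcome". Section 4 plans "to analyze perioperative anesthetic factors that affected their primary outcome", and Section 8 (Outcomes) agrees; there the primary outcome is survival, ICU admission and length of stay together.

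On size, Section 6 says only that "Planned sample size will include all COVID-19 positive and negative cases". Sections 6 and 7 fix the window (April 1 to November 16, 2020), one hospital and consecutive adults. No number of patients, deaths or expected mortality is given.

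On candidate factors, Section 6 (Variable Abstraction) states: "Patient demographic and clinical data will be collected including age, morbidities, presenting symptoms, physical examination, laboratory investigations, intraoperative data", and continues with further items. It adds that "the type of anesthesia is also included as factor for further complications ex general anesthesia, spinal or combined spinal epidural type".

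**The concern.** A logistic model for death draws its information mainly from the number of deaths. Here that number is unknown and cannot be increased, because the window is closed, while the list of possible covariates has no limit. If one category of a factor contains no deaths, its maximum-likelihood odds ratio runs to zero or infinity and the software output for it is unusable. Anaesthesia type is exposed to this because three categories split the deaths three ways.

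Two consequences would follow if deaths are few. The model might yield no usable odds ratio for a named factor of interest. And a factor that fails to reach P<0.05 because the data are sparse might be reported as having no effect. Because the data already exist, covariates could also be chosen after the outcomes have been seen.

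**Working it through.** **No figure to reproduce.** The documents give no n, deaths, mortality, power or effect size. All inputs below are assumptions, shown over a range.

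**Assumed inputs.** General 50%, spinal 30%, combined spinal epidural 20%, with no effect of anaesthesia type on death; COVID positive 20%, odds ratio 2; age odds ratio 1.5 per SD. Four coefficients: age, COVID status, spinal, combined spinal epidural.

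**Step 1: an anaesthesia group without deaths.** With D deaths spread at random over the groups, inclusion-exclusion gives P(some group has none) = 0.7^D + 0.8^D − 0.3^D − 0.2^D (the two 0.5^D terms cancel).
- D=5: 0.168 + 0.328 − 0.002 − 0.000 = 0.493
- D=10: 0.028 + 0.107 = 0.136
- D=20: 0.001 + 0.012 = 0.012

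**Step 2: add COVID status.** At low mortality the COVID-positive share of deaths is about 0.2×2/(0.2×2+0.8) = 1/3, so P(no COVID-positive death) is about (2/3)^D: 0.132, 0.017 and 0.000. The chance that either factor fails is then about:
- D=5: 1 − 0.507×0.868 = 0.56
- D=10: 1 − 0.864×0.983 = 0.15
- D=20: 1 − 0.988×1.000 = 0.01

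**Step 3: simulation.** 1,000 series per cell with exactly 5, 10 or 20 deaths, separation tested by linear programming, gave 58.2/16.6/1.6% at n=100 and 58.2/16.3/0.5% at n=200. A separate rerun gave 56-58%, 13-16% and about 1%. The hand calculation agrees.

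**Step 4: by n and mortality.** Share of series with at least one non-finite odds ratio, among those with at least one death (four coefficients, 600 series per cell):

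| n | 2% | 5% | 10% | 20% |
|---|---|---|---|---|
| 50 | 97.7% | 90.5% | 64.6% | 19.0% |
| 100 | 89.8% | 55.6% | 21.3% | 2.7% |
| 200 | 71.8% | 19.3% | 2.7% | 0.0% |

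A series with no deaths at all has probability (1−p)^n. At 2% mortality that is 0.98^50 = 36% and 0.98^100 = 13%.

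**Step 5: does penalisation help?** Over assumed n of 50 to 200, mortality of 5 to 10% (n=50 at 5% only) and anaesthesia odds ratios of 1 and 0.5, Firth estimates were finite in every series. The 95% profile intervals covered the true value in 95.2-99.0% of series. Precision is still poor: the median ratio of upper to lower limit for spinal was 79.5/23.0/10.6 at 5/10/20 deaths (n=100) and 66.4/21.2/8.9 (n=200).

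**Step 6: significance.** Two-sided Fisher P for zero deaths in one group:
- Equal groups, 5 versus 0: 0.0502 (n=50), 0.0563 (n=100), 0.0594 (n=200).
- 30% group, 9 deaths elsewhere: 0.043, 0.054 and 0.060 at n=50, 100 and 200. With 10 deaths: 0.030 (n=100) and 0.034 (n=200).
- 20% group: P<0.05 is first reached at 15 deaths (13 at n=50).

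With half the patients exposed, n=200 and a true odds ratio of 1/3, power is 22% with 10 deaths and 54% with 20.

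**The case against.** Deaths may be plentiful, and then the planned model is sound. That stands: at 20 deaths the problem nearly disappears. A reader might infer that the plan will fail, but the documents give no death count that would support this.

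A reader might also take 10 deaths as a derived minimum, below which no model should be fitted. The figures do not support that. The number needed for P<0.05 with no deaths in a group changes with n and group size (9, 10, 13 or 15 in Step 6), and at 10 deaths separation still occurs in 13-17% of series. Firth fits kept about nominal coverage even at n=50 with 5% mortality, where 2.5 deaths are expected. Any minimum is a choice.

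The significance argument runs in one direction only. With 30% spinal, three deaths that all fall under spinal give P of about 0.025. So P<0.05 is out of reach for some splits, not in general.

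It is tempting to call anaesthesia type the factor that the study is about. Section 6 names it as a factor for further complications and gives the categories as examples; Sections 1 and 3 seek perioperative factors generally; and where Sections 4 and 8 do say anaesthetic factors, survival is one of three outcomes. It is a named factor of interest, no more. ICU admission may have more events and is outside this point.

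Finally, Section 9 already plans frequencies and percentages for outcomes, and its wording is permissive. So part of a descriptive fallback exists, but nothing says when to use it.

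**Conclusion.** The omission is real and the point holds in conditional form. For the survival model, nothing in the documents ties model size to deaths or says what to do when deaths are few or absent. If that happens, the plan as written can produce non-finite odds ratios: more often than not at about 5 deaths, in roughly one series in seven at 10, and rarely at 20. These rates rest wholly on assumed group sizes, effects and a four-coefficient list at n=100 or 200; a longer list would raise them. The change is worth making because it is cheap and leaves the planned analysis untouched when deaths are sufficient. Confidence is medium, since the documents do not allow the likely death count to be judged.

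**What to change.** Add to Section 9, for the survival model:

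1. Before outcomes are examined, fix a short covariate list that keeps anaesthesia type, counted as at least two coefficients, and state which deaths count (for example in-hospital), so that events can be counted.
2. Use Firth-penalised logistic regression with profile-likelihood intervals if separation occurs or deaths are few relative to coefficients, for example fewer than 5 per coefficient (4 × 5 = 20 deaths for a four-coefficient list). Otherwise the planned logistic regression stands.
3. If there are no deaths, or too few for a useful interval, report n, deaths, deaths by anaesthesia type, and mortality with an exact 95% CI (5 deaths in 100 would give 1.6% to 11.3%). If a minimum death count is set, for example 10, present it as the investigators' choice.
4. Report odds ratios with 95% CIs, and do not read a non-significant factor as having no effect.

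Cost: a few sentences and no new data; a package outside SPSS 22 and Epi-info for the Firth fit; fewer factors in the adjusted model; and wide intervals when deaths are few. If a minimum of 10 were chosen, the survival-factor aim would become descriptive in 97% of series at n=100 with 5% mortality, in about 45% at n=100 with 10% or n=200 with 5%, and in under 1% at n=100 with 20% or n=200 with 10% (binomial, assumed inputs). The investigators should weigh that before setting one.
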